A) To determine how intestinal epithelial integrity (assessed via characterization of intestinal tissue tight junctions and also via GI permeability probe studies) and microbial translocation relate to measures of monocyte and macrophage activation and to measures of CVD risk utilizing functional imaging (by ¹⁸fluorodeoxyglucose positron emission tomography (FDG-PET) and structural (cardiac CTA) cardiac imaging to assess arterial inflammation and coronary atherosclerotic disease.

B) Trancriptome analysis of circulating monocytes using RNA-Seq to identify distinctive genomic signatures in monocytes of HIV-infected patients with greatest amount of coronary atherosclerosis detected on CTA compared to HIV-infected patients without atherosclerosis to elucidate novel biological pathways involved in atherogenesis in HIV disease. These pathways will also be compared to dysregulated pathways in HIV patients with greatest degree of intestinal permeability/microbial translocation compared to patients with the least. We hypothesize that biological pathways in monocytes stimulated by microbial translocation will be similar to pathways activated in monocytes of patients with greatest degree of CVD.

Aim 2: Determine the effects of a glucagon-like peptide-2 analog, teduglutide, on intestinal epithelial integrity, on microbial translocation across the gut lumen, on markers of innate immune system activation including the monocyte transcriptome, and on arterial inflammation in a 6-month randomized, double-blind placebo-controlled proof of concept trial in HIV-infected individuals.

Exploratory Aim: An additional exploratory aim is to study the interrelationships between cerebral glucose metabolism measured by FDG-PET of the brain (a proxy for neural activity), cognitive performance and arterial inflammation as well as gut microbial translocation in patients living with HIV.

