To answer Aim 1B, transcription profiling by RNA-Seq will be performed on a subset of participants. Seven patients with greatest degree of coronary atherosclerosis vs. 7 patients with the least amount of coronary atherosclerosis and 7 patients with greatest degree of microbial translocation vs. 7 patients with the least amount of microbial translocation. Both groups will be matched by age and traditional cardiovascular risk factors. As Verdugo *et al* recently found that smoking can affect the monocyte transcriptome⁴², we will exclude patients who are active smokers in Aim 1B. Transcription profiling of monocytes by RNA-Seq will also be performed in a subset of 7 participants in the active teduglutide arm who have the greatest amount of coronary atherosclerosis before and after their teduglutide treatment in the Randomized Study of Teduglutide vs. Placebo.

[figure not shown]
To answer Aim 2, we propose a randomized, double-blind, placebo-controlled trial to assess the effects of treatment with teduglutide 0.05 mg/kg/day for 6 months duration compared to placebo. Recruitment for this interventional trial will occur concurrently with the cross-sectional study in Aim 1A. Participants who are recruited for the randomized study will complete Baseline Studies Part 1 and Part 2 as their baseline for the randomized study (see Figure 1a). Participants who are recruited for the neurological substudy will complete Visit A and B (see Figure 1b). *This design is intended to minimize risk of study procedures to patients by maximizing use of data and also to improve efficiency in recruitment.* Thus, the participants in the randomized study will also complete the cross-sectional study. These participants undergo the same baseline procedures again at the end of the 6-month intervention for their end-of-study procedures. We will refer to the procedures involved in the randomized study as the **Randomized Study of Teduglutide vs. Placebo.**

Figure 1a.

*Only for healthy controls and HIV+ subjects who will complete Baseline Study Part 2. Transcriptomic profiling (RNA-SEQ) will be performed on stored samples after the study has been completed.

Figure 1b.

[figure not shown]
III. Subject Selection

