Medical Record Review: Medical records will be reviewed for relevant clinical data for subjects who are currently followed at MGH or BWH for clinical care. Subjects who receive clinical care from external providers will be asked to sign a Release of Information form. We will request and/or review relevant medical history, laboratory results and treatment history for HIV and/or Hepatitis B and C.

Visit 3 (Colonoscopy)

- 1. Colonoscopy will be performed in the MGH GI endoscopy suite and performed according to standard MGH clinical colonoscopy protocol.
- 2. Blood draw for isolation of cells to be used for immunological studies.

Follow-up Phone call:

The study coordinator or a study investigator will have a follow up phone call with subjects the day after the colonoscopy procedure. The purpose of the call will be to assess how the participant tolerated the procedures and whether an adverse event occurred. If an adverse event occurred, a study physician will speak with the participant. If a study coordinator calls the subject, she/he will inform the subject during the call that a study doctor will call them if they wish.

If eligible, subject will be randomized to either teduglutide or placebo and return for:

Visit 4 (Baseline visit):

- 1. Meet with investigator for dispensing of study drug (including administration of first dose and 30 minute observation)
- 2. Serum HCG will be obtained STAT as a pregnancy test for women prior to FDG-PET
- 3. Blood drawing for RNA-sequencing, and for sera and plasma to be frozen for assays to be run in batch using kits.
- 4. FDG-PET/CT
- 5. Neurocognitive Test Battery administered between 18F-FDG tracer injection and prior to FDG PET/CT scan.
- 6. Center for Epidemiological Studies-Depression Scale (CES-D).
- 7. Cognitive Function Instrument (CFI), and Patient's Assessment of Own Functioning Inventory (PAOFI) Questionnaire.

Visit 4 may be conducted before Visit 3, depending on scheduling availability.

Follow up safety visit 1 month after randomization and then at month 3:

- 1. Blood draw for safety labs, comprehensive metabolic panel, amylase, lipase, CBC with differential, and blood samples will also be stored for biomarkers to be run in batch (sCD14, LPS, I-FABP, sCD163)
- 2. Assess for side effects
- 3. Assess for change in medical problems or medications
- 4. Urine HCG for women
- 5. PAOFI and CES-D at month 3

Final visits at month 6:

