1. Repeat all procedures performed at Visits 1, 2, 3 and 4 in four separate visits

Fecal occult blood testing at 1 year:

Participants who participated in the Randomized Study of Teduglutide vs. Placebo will be given the fecal immunochemical test kit to be performed at home at 1 year from the starting of study medication teduglutide or placebo. They will be asked to return this to the laboratory for processing. If the result returns abnormal, we would recommend follow-up with their primary care physician and also offer to the participant to perform a colonoscopy using study funds if their primary care physician agrees.

For Participants in Baseline Study Part 1 (Biomarkers, Immunology and Intestinal Permeability Studies) only:

All potential subjects will complete a brief telephone screen followed by a clinical evaluation to determine eligibility for the study. The first clinical evaluation will be performed in the Clinical Research Center (CRC) at Massachusetts General Hospital (MGH) during the screening visit. Written informed consent will be obtained from each subject upon arrival to the CRC during the first screen visit and prior to testing. The consent form will be discussed with the subject by a licensed investigator (MD or NP).

Visit 1:

- 1. Participant will meet with study investigator (M.D. or N.P.) to review the consent form and signing of informed consent
- 2. Detailed medical history, including assessment of history of anti-retroviral use, hepatitis status, nadir CD4 count, gastrointestinal disease, prior history of CNS opportunistic infections and risk factors for cardiovascular disease, including smoking history, family history, and history of recreational drug use
- 3. Physical examination
- 4. Fasting blood will be obtained for glucose, comprehensive metabolic panel, CBC plus differential, high-sensitivity C-reactive protein, insulin, hemoglobin A1C, lipids, T-cell subset, and HIV RNA (for HIV-infected patients) and HIV ELISA test (for HIV-negative controls). Additional blood will be collected for isolation of peripheral blood mononuclear cells for immunological studies, serum and plasma to be frozen and stored.

Visit 2:

- 1. Intestinal Permeability Study (sugar probe solution drink and urine collection)
- 2. Twenty-six milliliters of blood (3 ACD tubes) will be collected for isolation of peripheral blood monocytes.
- 3. Bionutrition:
 - -Anthropometry (weight, height, waist and hip circumference measurements)

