Sample Size Determination: With 30 patients in each group and up to 10% attrition (i.e. evaluable n=27/group), this trial can detect at least a between group difference of 0.2244 in the two within person TBR mean changes at a 5% significance level with 85% power by a two-sided independent samples t-test. This assumed that the standard deviation of the within subject TBR change is 0.27, which was estimated from our prior study at MGH study of similar patient population²⁸ of which the observed mean \pm (standard deviation) of the cross sectional TBR data was 2.24 (\pm 0.35) and the assumed pre- to post intervention longitudinal correlation was 0.7. This detectable effect size is close to 10% of the baseline mean 2.24, and we anticipate that the placebo group will show no change (or even increase its mean value). The effect size of 10% is of clinical significance as it is similar to the amount of decrease seen with statin treatment for 3 months⁵⁹, the most effective medical therapy we have to date for treatment of atherosclerotic disease and prevention of MI.

VII. Risks and Discomforts

Colonoscopy: Colonoscopy are generally safe procedures and complications are rare. Given the underlying HIV infection of the study participants, there is potential for the sequellae of the endoscopy complications outlined below to be more serious and more difficult to treat.

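### Aim 2 promises teduglutide's effect on the monocyte transcriptome, but before/after RNA-Seq is planned only in seven active-arm participants, so for this one outcome a drug effect cannot be separated from other change over time

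*Combined protocol and SAP*

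**What the plan says.** Aim 2 (protocol, II. Specific Aims) sets out to determine the effects of teduglutide, among other outcomes, "on markers of innate immune system activation including the monocyte transcriptome", in a six-month double-blind placebo-controlled trial.

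The paragraph on Aim 1B under Research Design says how the transcriptome will be measured. Besides two cross-sectional contrasts of 7 vs 7 (most vs least coronary atherosclerosis; most vs least microbial translocation), it adds RNA-Seq "in a subset of 7 participants in the active teduglutide arm who have the greatest amount of coronary atherosclerosis before and after" teduglutide treatment. No such subset is described for placebo. The list of RNA-Seq subsets in III. Subject Selection leaves the before/after subset out altogether.

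The samples themselves are not limited to one arm. Visit 4 includes "Blood drawing for RNA-sequencing, and for sera and plasma to be frozen", and the month-6 instruction is "Repeat all procedures performed at Visits 1, 2, 3 and 4 in four separate visits". The note to Figure 1a says: "Transcriptomic profiling (RNA-SEQ) will be performed on stored samples after the study has been completed".

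In the statistical section, the RNA-Seq text covers Aim 1B only: LIMMA, multiplicity correction, and a power statement for 7 vs 7. The Aim 2 text plans a between-arm t-test on changes for secondary endpoints, including innate immune activation. Neither part describes an analysis or gives power for the before/after subset.

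**The concern.** The aim is worded as a treatment effect from a randomised comparison, but the measurement plan is a one-arm before/after study. Anything that changes over six months for reasons other than the drug is counted with it: time, visit conditions, and storage, since baseline samples will have been frozen about six months longer than month-6 samples. The seven are also picked for an extreme value of plaque, so expression related to plaque may drift back towards the average without treatment.

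The between-arm test that the SAP promises for markers of innate immune activation cannot be run on the transcriptome without placebo libraries. Followed as written, one named part of Aim 2 could be reported as an effect of teduglutide without a control to support it.

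**Working it through.** **1. What the plan would sequence.** Aim 1B: 4 groups × 7 = up to 28 libraries. Before/after subset: 7 active × 2 = 14. Total up to 28 + 14 = 42, with no placebo month-6 library.

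**2. The plan's only RNA-Seq power figure.** For 7 vs 7 at 2.7 SD and per-gene alpha 0.0011, the SAP states at least 80%. Noncentrality is 2.7 × √(7/2) = 5.05.
- Ordinary two-sided t, 12 df: 74.8%.
- LIMMA-type moderated t, adding 2 or 4 assumed prior df: 79.4% or 82.6%.
- One-sided t: 83.8%. Normal approximation: 96.3%.

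The stated figure is about right under the test the SAP names, given a few prior df. The SAP states no prior df, so 2-4 is an assumption.

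**3. What a control costs in power.** Take an effect of 2.7 SD *of within-person change*. The 2.7 is borrowed from Aim 1B, because no SD of change in expression is given. Paired test, n = 7: noncentrality 2.7 × √7 = 7.14, on 6 df plus prior df. Difference in change, 7 vs 7: noncentrality 5.05, on 12 df plus prior df.

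| Test | Active only, paired | Active vs placebo, change | Loss |
|---|---|---|---|
| Ordinary t | 78.9% | 74.8% | 4.1 points |
| Moderated, 2 prior df | 92.7% | 79.4% | 13.3 points |
| Moderated, 4 prior df | 97.1% | 82.6% | 14.5 points |

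The two columns test different things: the paired test asks whether expression changed, and the two-arm test asks whether it changed more on drug.

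**4. Dependence on pre/post correlation.** If 2.7 is instead read in cross-sectional SDs, the SD of change is SD × √(2(1−ρ)). For ρ = 0, 0.5, 0.7 and 0.9 (assumed; the documents give 0.7 for TBR only), the 7 vs 7 comparison of change has 33%, 75%, 96% and over 99% power with ordinary t-tests. Adjusting for baseline gives 75%, 89%, 98% and over 99%.

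**5. What a control costs in libraries.** Seven placebo pairs add 7 × 2 = 14, taking the total to 42 + 14 = 56 without reuse. With 30 per arm, about 7 × 0.5 = 3.5 of the overall top seven for plaque would be on placebo and already have an Aim 1B baseline library. The addition then falls to about 14 − 3.5 = 10.5. The Aim 1B smoker exclusion and matching would reduce this overlap, and the documents do not state it.

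**6. Illustration of the attribution problem.** With no shift, the paired test at alpha 0.0011 flags 27,000 × 0.0011 ≈ 30 genes. If a non-drug shift of 0.5 or 1 SD of change affected every gene, the per-gene probability would be 0.0083 or 0.0559, which gives about 225 or 1,500 genes. The shift is assumed and comes from nowhere in the documents.

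**The case against.** The before/after subset is an add-on in the Aim 1B paragraph of a proof-of-concept trial, and seven people would be exploratory under any design. That is fair, and it limits the weight of the point, but Aim 2 still names the transcriptome as something the randomised trial will answer.

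Three stronger readings are tempting and are not supported.

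*That the trial gives up its placebo control.* It does not. The primary outcome, TBR, and the secondary permeability, translocation and innate-activation endpoints are compared between arms.

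*That a placebo comparison of change needs no more sequencing.* One could take month-6 libraries from 7 active and 7 placebo participants who already have an Aim 1B baseline library, and again count 28 + 14 = 42. But that credits reuse to the alternative and none to the plan, whose seven would also overlap with Aim 1B (about 14 − 3.5 = 10.5 new libraries). It also needs seven per arm among Aim 1B participants. If allocation is unrelated to Aim 1B membership, the chance is about 24% with 14 distinct randomised people and 95% with 20, and the documents do not say how many there will be. Some of those people are chosen for the *least* disease, which changes the question. Splitting 14 libraries into 4 vs 3 pairs leaves about 10% power at ρ = 0.5 (ordinary t). A month-6-only comparison of 7 vs 7 does use 14 libraries, but gives up the before/after pairing.

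*That the active-only design will produce hundreds of false findings.* The 225 to 1,500 genes depend wholly on an assumed shift in all genes. The attribution problem does not need that figure.

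**Conclusion.** The point holds for the transcriptome outcome of Aim 2 only. As planned, a change in expression in the seven active-arm participants cannot be attributed to teduglutide, because no placebo participant is sequenced after treatment. This follows from the design and rests on no numerical assumption.

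The remedy is feasible because RNA blood is collected at baseline and month 6 without restriction by arm and is sequenced from storage after the study. It is not free: up to 14 extra libraries, and a power loss of about 4 points with ordinary t-tests or 13 to 15 points under a moderated test. Those power figures assume 2.7 SD of change, alpha 0.0011 and, for LIMMA, 2-4 prior degrees of freedom.

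**What to change.** Amend the RNA-Seq paragraph under Research Design, the subset list in III. Subject Selection, and the SAP.

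1. Sequence stored baseline and month-6 samples from 7 placebo participants as well as the 7 active ones. Choose both sets by the same rule, applied to the *baseline* CTA; the protocol does not say which scan defines the greatest atherosclerosis.
2. Name the analysis: between-arm difference in change, fitted with LIMMA and using the multiplicity correction already planned. Say that it is exploratory.
3. Reuse Aim 1B baseline libraries where the same person has one.

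Cost: protocol and SAP wording and up to 14 libraries (fewer with reuse), with the lower power shown above. No new visit, procedure or blood draw is needed.

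If placebo libraries cannot be afforded, state in the SAP that the active-only subset describes within-arm change and will not be reported as an effect of teduglutide, and qualify the Aim 2 wording to match. That costs only the wording.

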- 13. Subject taking any of the following medications: systemic steroids (inhaled or nasal steroid therapy is permitted), interleukins, systemic interferons (e.g. local injection of interferon alpha for treatment of HPV is permitted), systemic chemotherapy including oral chemotherapeutic agents, methotrexate, octreotide, growth hormone, antiarrhythmics including digoxin, antiepileptics, immunosuppressants, vancomycin, rifampin, aminoglycosides, clonidine, prazosin, lithium and ritonavir-boosted lopinavir (Kaletra).
- 14. Subjects receiving high dose statin therapy (a stable low or moderate dose of statin is permitted)
- 15. Initiation of statin therapy or change in statin dose <90 days prior to entry
- 16. Subject has had two or more of the same endoscopy procedures (sigmoidoscopy, or colonoscopy) within the past 12 months for clinical purposes or other research studies.
- 17. Body weight greater than 350 lbs
- 18. Active illicit drug use
- 19. Patients who report any significant radiation exposure over the course of the year prior to randomization. Significant exposure is defined as:
 - a) More than 2 percutaneous coronary interventions (PCI) within 12 months of randomization
 - b) More than 2 myocardial perfusion studies within the past 12 months
 - c) More than 2 CT angiograms within the past 12 months
 - d) Any subjects with history of radiation therapy
- 20. Patients already scheduled or being considered for a procedure or treatment
 - a) requiring significant radiation exposure (e.g., radiation therapy, PCI, or catheter
 - b) ablation of arrhythmia) within 12 months of randomization
- 21. History of malignancy in the last 5 years, with the exception of surgically cured non-metastatic

non-melanoma skin cancers

22. Prior recipient of a HIV vaccine

Inclusion/Exclusion Criteria for HIV-negative Controls

For the HIV-negative control group in the parent study and the neurological substudy, we will recruit a total of 35 men and women without known HIV disease with the same inclusion and exclusion criteria other than the inclusion criteria of presence of HIV infection and stable antiretroviral therapy.

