Attempts will be made to recruit patients who will be undergoing endoscopy and/or colonoscopy as part of their routine care (e.g., patients undergoing screening colonoscopies).

In many cases, the patient's primary/specialist health care provider will initially inform the patient of the study, if it appears that the subject would be an appropriate candidate for the study. Individuals enrolled in other studies at the MGH Program in Nutritional Metabolism or at the Ragon Institute who have indicated a willingness to participate in additional studies for which they may be eligible may also be contacted regarding this study. Subjects may also be recruited using the Partners' Research Patient Data Registry (RPDR). Additionally, some subjects may be self referred in response to IRB approved recruitment tools such as flyers, posters, website postings, or advertisements.

After referral is received regarding a potential subject or a potential subject contacts the study staff, the study will be thoroughly explained and a pre-screening eligibility questionnaire will be administered by a member of the study staff during a pre-screening phone call. A consent form (containing information about the procedures) will be sent to the potential subject for review if they wish to receive this information beforehand. The information in the completed phone eligibility screening form will be reviewed for approval by the study physician before the various appointments and accommodations are scheduled. All subjects will be given adequate time to consider participation and ask questions about the study.

Written informed consent will be obtained by a licensed physician investigator at the initiation of the screening visit. The study investigator will review the consent form with the potential subject in detail. After all questions are answered to the satisfaction of the subject, the subject and investigator will sign the consent form. A copy of the signed consent form will be given to the subject to keep. The consent form will be in accordance with the guidelines of and approved by the Partners Human Research Committee. Eligible participants who consent to participate in the Randomized Study of Teduglutide vs. Placebo will undergo randomization to active study drug vs. placebo.

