Intervention in Randomized Study of Teduglutide vs. Placebo: Teduglutide 0.05mg/kg body weight subcutaneously once a day vs. placebo of identical appearance from baseline to 6-month final visit. Dosing of teduglutide is based on published randomized placebo-controlled trial of teduglutide in patients with short bowel syndrome⁴¹. At initiation of study medication, half of the dose (0.025mg/kg body weight subcutaneously once a day) will be administered in the first week. If participant tolerates the study medication, the dose will be increased to the full dose (0.05mg/kg body weight subcutaneously once a day). If the participant develops gastrointestinal side effects while on the full dosage of the study drug, the study team will instruct the participant to return to the half dose of 0.025mg/kg.

Method of Randomization: Permuted blocks randomization with randomly varying block sizes will be implemented. All investigators and patients will remain blinded to drug assignment.

Only HIV-positive participants will enter the **Randomized Study of Teduglutide vs. Placebo. HIV**negative controls will only participate in the baseline cross-sectional study (part 1 and 2 of baseline).

V. Study Procedures

All potential subjects will complete a brief telephone screen followed by a clinical evaluation to determine eligibility for the study. The first clinical evaluation will be performed in the Clinical Research Center (CRC) at Massachusetts General Hospital (MGH) during the screening visit. Written informed consent will be obtained from each subject by a physician investigator upon arrival to the CRC during the first screen visit and prior to testing.

Visit 1 (Screen Visit):

- 1. Participant will meet with study investigator to review the consent form and signing of informed consent
- 2. Detailed medical history, including assessment of history of anti-retroviral use, hepatitis status, nadir CD4 count, gastrointestinal disease, prior history of CNS opportunistic infections and risk factors for cardiovascular disease, including smoking history, family history, and history of recreational drug use
- 3. Physical examination

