As teduglutide was approved by the FDA for short gut syndrome in December 2012, it is still fairly new to market, so there may be yet some unknown side effects outside of those reported in the clinical trials, but data is being collected in an FDA-required postmarketing study of patients with short bowel syndrome treated with teduglutide in the clinical setting to further evaluate the drug's long-term safety. In our proposed randomized study, we will monitor patients at each visit for possible symptomatic side effects. In addition, we will also follow the necessary recommended safety testing at baseline and at safety interim visits in the study. Patients with known malignancy within the last 5 years, history of colon cancer, or first degree relative with colon cancer will be excluded from the study. Screening colonoscopy will identify participants with previously undiagnosed colon cancer, whom we will exclude from the interventional study. All interventional study participants will undergo a colonoscopy at the end of the study. Women who are pregnant, planning on becoming pregnant, or are breastfeeding will be excluded from the study.

Radiation Risks:

The estimated median dose of CCTA is 4 mSv. Individual dose will vary, as each exam is tailored to the subject's size, heart rate, and rhythm. This tailored approach along with the state-of-the-art dose reduction techniques described above allow the dose to be substantially lower than historically reported median CCTA doses (please see references from MGH below).

References for CCTA dose at MGH:

Ghoshhajra, B. B., Engel, L.-C., Major, G. P., Goehler, A., Techasith, T., Verdini, D., et al. (2012). Evolution of coronary computed tomography radiation dose reduction at a tertiary referral center. The American journal of medicine, 125(8), 764–772. doi:10.1016/j.amjmed.2011.10.036

Engel, L.-C., Lee, A. M., Seifarth, H., Sidhu, M. S., Brady, T. J., Hoffmann, U., & Ghoshhajra, B. B. (2013). Weekly dose reports: the effects of a continuous quality improvement initiative on coronary computed tomography angiography radiation doses at a tertiary medical center. Academic Radiology, 20(8), 1015–1023. doi:10.1016/j.acra.2013.04.012

Ghoshhajra, B. B., Engel, L.-C., Károlyi, M., Sidhu, M. S., Wai, B., Barreto, M., et al. (2012). Cardiac Computed Tomography Angiography With Automatic Tube Potential Selection: Effects on Radiation Dose and Image Quality. Journal of thoracic imaging, 1–9. doi:10.1097/RTI.0b013e3182631e8a

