Radiation exposure for a low dose CT scan of the abdomen is about 0.10 mSV per slice.

For FDG-PET/CT, the administered dose from F-18 FDG for a typical cardiac study is 370 MBq (10 mCi) and the effective dose for an attenuation correction scan of head/neck/chest/upper abdomen is about 2.8 mSv. The total effective dose from two FDG-PET/CT studies would be 20 mSv.

The total radiation dose associated with this study is approximately 28 mSv and is about the same as one would normally receive in approximately 9 years from background radiation.

Blood drawing:

The maximum total blood drawn for a patient completing the 6 month long interventional study is approximately 502 ml for participants with HIV and 226 ml for participants without HIV. There will be minimal risk and discomfort associated with blood drawing and IV placement. The risks of these procedures are minor bruising or bleeding at the site of the blood draw or IV catheter, nausea from the glucose infusion, and lightheadedness from the blood draws.

The maximum total blood drawn for a patient completing only the cross-sectional substudy is approximately 150 mL.

For each participant, blood will not be drawn more than twice per week and the total amount will not exceed 550mL in an 8-week period. Blood sampling exceeding 200mL will not be drawn at any one point in time.

Genetic Research Studies:

Genetic research studies may create special risks to human subjects and their relatives. These involve medical, psychosocial and economic risks, such as the possible loss of privacy, insurability and employability, change in immigration status and limits on education options, and may create a social stigma. Knowledge of one's genetic make-up may also affect one's knowledge of the disease risk status of family members. To minimize the risks associated with genetic testing, no results will be filed in the subject's medical record and no research results will be given to subjects or healthcare providers.

CT contrast medium:

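### Exclusion 19 omits FDG-PET/CT, this study's largest radiation dose source, from its list of significant prior exposure, and parts of items 19 and 20 are dated to a randomization that the imaged controls never have

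*Combined protocol and SAP*

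**What the plan says.** - **Section III, exclusion item 19.** The lead-in is "Patients who report any significant radiation exposure over the course of the year prior to randomization. Significant exposure is defined as". Four entries follow. For PCI, entry 19a sets a limit of two, counted in the 12 months around randomization. Perfusion imaging (19b) has the same limit, but over the preceding year and with no mention of randomization. Entry 19c takes that same form for CTA: "More than 2 CT angiograms within the past 12 months". Under 19d, radiation therapy at any time in the past excludes. There is no catch-all entry and no cumulative limit.
- **Section III, exclusion item 20.** This looks forward. It excludes people scheduled or considered for a procedure with significant radiation within 12 months of randomization, and gives examples only.
- **Section VII, Radiation Risks.** On coronary CTA the section says "The estimated median dose of CCTA is 4 mSv". For PET imaging, its figure covers the baseline and final scans together: "The total effective dose from two FDG-PET/CT studies would be 20 mSv". An abdominal CT slice is put at about 0.10 mSv, and the study total at approximately 28 mSv.
- **Section III, HIV-negative controls.** Controls in the parent study and the neurological substudy follow the same exclusions, apart from the HIV-specific entry requirements. Participants in Baseline Study Part 1 only have a separate list without radiation items, and have no CT or PET.
- **Section IV, Method of Randomization.** Only HIV-positive participants are randomized; on the others the text reads "negative controls will only participate in the baseline cross-sectional study (part 1 and 2 of baseline".
- **Section IV, recruitment.** Those who may be approached include "Individuals enrolled in other studies at the MGH Program in Nutritional Metabolism or at the Ragon Institute", if they have said they are willing to join further studies.

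**The concern.** Item 19 defines significant exposure; it does not merely illustrate it. A procedure that is not on the list does not count, however often it was done. The omitted procedure is the one that carries most of this study's own dose. Applied as written, the rule can turn away a person with a smaller prior-year dose and accept one with a larger dose, who may then receive about 28 mSv more in the randomized study.

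The second problem is the reference date. For people who are imaged but never randomized, any clause that counts 12 months from randomization cannot be applied literally. Staff would have to choose a date themselves.

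What is at stake is participant safety and uniform application of eligibility. No endpoint, sample size, power or significance level is affected.

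**Working it through.** **1. Reproduce the protocol's total.** A randomized participant has every baseline procedure twice: two coronary CTAs, two FDG-PET/CTs and two abdominal slices.

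2 × 4 + 20 + 2 × 0.10 = 28.2 mSv, or 28.0 without the slices. This agrees with the stated figure of about 28.

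**2. Dose per scan and share.** FDG-PET/CT: 20 / 2 = 10 mSv each, which is 10 / 4 = 2.5 times a study CTA. Its share of the total is 20 / 28 = 71%.

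**3. Apply item 19 to two histories.** Let d be the dose of a prior CTA and p that of a prior PET/CT.

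- History A, three CTAs: 3d. Excluded under 19c.
- History B, two CTAs and two PET/CTs: 2d + 2p. Admitted, since two CTAs are within the limit and PET/CT is not counted.

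B exceeds A when 2d + 2p > 3d, that is when d < 2p. With p = 10 the condition is d < 20 mSv.

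| CTA dose d (mSv) | A, excluded: 3d | B, admitted: 2d + 20 |
|---|---|---|
| 4 (site median) | 12 | 28 |
| 10 (assumed) | 30 | 40 |
| 20 (break-even) | 60 | 60 |

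**4. PET/CT alone against CTA alone.** This comparison is more sensitive to d. Three CTAs fall below two PET/CTs only if 3d < 20, so d < 6.7 mSv. They fall below three PET/CTs only if 3d < 30, so d < 10 mSv.

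**5. Reference dates for controls.** Imaged controls: 10 (Part 2) + 15 (neurological substudy) = 25 of the 35 controls. Each has one CTA, one PET/CT and one abdominal slice: 4 + 10 + 0.1 = 14.1 mSv.

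| Clause | Reference date | Usable for a control? |
|---|---|---|
| 19 lead-in | year before randomization | no |
| 19a, PCI | 12 months of randomization | no |
| 19b, perfusion studies | past 12 months | yes |
| 19c, CT angiograms | past 12 months | yes |
| 19d, radiation therapy | any history | yes |
| 20, planned procedures | 12 months of randomization | no |

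For randomized participants too, the date falls after exposure has begun: the study CTA is at Visit 1, and randomization follows Visit 3.

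**The case against.** **The 4 mSv may not describe prior scans.** It is an estimated median for this study's coronary CTA, and the protocol calls it well below historical values. Item 19c counts any CT angiogram, from any site. This stands against the comparison of PET/CT alone with CTA alone, which reverses at 6.7 or 10 mSv. It does not overturn the mixed history, which holds up to 20 mSv per CTA.

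**The controls do have a window.** A reader might infer from the word randomization that items 19 and 20 have no usable date at all for the 25 controls. The text does not support that: 19b and 19c look back over the past 12 months and 19d needs no date. The gap is confined to the lead-in, 19a and item 20.

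**No source of such candidates is shown.** A reader might infer that participants in the earlier FDG-PET study behind the TBR assumptions are a likely route. That study was published in 2012 and this protocol version is dated November 2018, so its scans cannot fall in the look-back year under this version. Section IV says that people in other studies may be contacted, not that those studies use PET. This objection stands: the frequency is unknown.

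**Other checks exist.** A physician reviews the phone screen, medical records are reviewed, and item 11 allows exclusion on the investigator's opinion. None of these mentions radiation, so they are partial safeguards. It is also true that the protocol nowhere states that item 19 is meant to cap cumulative dose; that purpose is inferred.

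**Conclusion.** The point holds as an eligibility and safety defect of modest size. FDG-PET/CT is missing from a closed definition although it supplies about 71% of the study's own dose, so any number of recent PET/CTs passes. The resulting inversion is 28 against 12 mSv at the site's CTA dose and 40 against 30 mSv at an assumed 10 mSv. It rests on 10 mSv per PET/CT, taken from the protocol's figure for two, and on a CTA dose below 20 mSv.

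The mixed reference dates leave three clauses (the lead-in, 19a and item 20) without a date for 25 controls.

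Two further readings are not supported. One is that the rule generally admits the more heavily exposed: that depends on the history and on the CTA dose, and no count of affected candidates is given. The other is a prior-plus-study total of 28 + 28 = 56 mSv as a typical figure. It is a constructed case for a randomized participant with history B; an imaged control receives about 14 mSv in the study.

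**What to change.** - Add FDG-PET/CT, both clinical and research, to the item 19 list, and reconcile the list with the doses in Radiation Risks. Any numerical limit is for the sponsor's radiation safety committee; none is proposed here. Item 16 already counts endoscopies from clinical care and from other research, so the wording has a precedent.
- Ask about prior PET/CT at the existing telephone screen.
- Use one look-back date throughout item 19 that applies to everyone imaged, for example the first study scan.
- Give item 20 a reference date for controls who are not randomized. Keep its forward window for randomized participants as it is: moving that window to the first study scan would make it end earlier for them, because Visit 1 imaging precedes randomization.

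Replacing the counts per modality by a single cumulative dose estimate is a possible alternative, but it is a design preference and is not needed to close the gap.

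The cost is a rewording of two criteria and one screening question. The downside is that a few people with a recent PET/CT become ineligible or must wait.
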